6.1.2. Exclusion Criteria

Participants are excluded from the study if any of the following criteria apply:

1. Known hypersensitivity to HCQ or other 4-aminoquinoline compounds
2. Currently hospitalized
3. Symptomatic with subjective fever, cough, or shortness of breath
4. Current medications exclude concomitant use of HCQ
5. Concomitant use of other anti-malarial treatment or chemoprophylaxis, including chloroquine, mefloquine, artemether, or lumefantrine.
6. History of retinopathy of any etiology
7. Psoriasis
8. Porphyria
9. Known bone marrow disorders with significant neutropenia (polymorphonuclear leukocytes <1500) or thrombocytopenia (<100 K)
10. Concomitant use of digoxin, cyclosporin, cimetidine, amiodarone, or tamoxifen
11. Known moderate or severe liver disease
12. Known long QT syndrome
13. Severe renal impairment

14. Use of any investigational or non-registered drug or vaccine within 30 days preceding the first dose of the study drugs or planned use during the study period

6.2. *Index Cases*

6.2.1. *Inclusion Criteria*

1. Men or women ≥ 18 years of age inclusive, at the time of signing the informed consent
2. Willing and able to provide informed consent
3. Currently diagnosed with known PCR-confirmed SARS-CoV-2 infection or is currently being assessed for COVID-19
4. A close contact is enrolled in the study

6.2.2. *Exclusion Criteria*

1. Currently hospitalized

6.3. *Screen Failures*

Screen failures are defined as participants who consent to participate in the clinical study but are not subsequently randomly assigned to study treatment. A minimal set of screen failure information is required to ensure transparent reporting of screen failure participants to meet the Consolidated Standards of Reporting Trials publishing requirements and to respond to queries from regulatory authorities. Minimal information includes demography, screen failure details, eligibility criteria, and any serious adverse event (SAE).

Individuals who do not meet the criteria for participation in this study (screen failure) can be rescreened if there is a change in their eligibility.

6.4. *Recruitment*

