8.1. Discontinuation of Study Treatment

Study treatment will be discontinued for the following reasons:

- Requirement for prohibited concomitant medications or other contraindication to HCQ
- Occurrence of an AE requiring discontinuation of study medication
- Request by participant to terminate study treatment
- Clinical reasons believed to be life-threatening by the physician, even if not addressed in [Section 7.2](#)

Participants who stop study treatment should continue study participation off study medication with continued evaluations as per the SoA. The reason for study medication discontinuation should be recorded.

Participants who are identified as SARS-CoV-2 positive by PCR at baseline should continue study therapy and study participation.

Participants with a clinical diagnosis of COVID-19 should continue on study therapy unless they are started on COVID-19 treatment outside of the study.

8.2. *Withdrawal from the Study*

- A participant may withdraw from the study at any time at his/her own request or may be withdrawn at any time for the following reasons:
 - At the request of the primary care provider if he/she thinks the study is no longer in the best interest of the participant
 - Participant is judged by the Investigator to be at significant risk of failing to comply with the provisions of the protocol as to cause harm to self or seriously interfere with the validity of the study results
 - At the discretion of the Institutional Review Board/Ethics Committee or government agencies as part of their duties, Investigator, or industry supporter
- If the participant withdraws consent for disclosure of future information, the sponsor may retain and continue to use any data collected before such withdrawal of consent.
- If a participant withdraws from the study, he/she may request destruction of any samples taken and not tested, and the Investigator must document this in the site study records.
- See SoA for data to be collected at the time of study discontinuation and follow-up and for any further evaluations that need to be completed.

8.3. *Lost to Follow-up*

A participant will be considered lost to follow-up if he/she is unable to be contacted by the study site.

The following actions must be taken if a participant fails to comply with required study procedures:

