3. GENERAL DATA ANALYSIS CONSIDERATIONS

3.1. ANALYSIS SET(S)

This section describes the cohorts for the primary, secondary and exploratory analyses described in this document.

Intention to Treat (ITT) Cohort: The ITT Cohort includes all contacts enrolled into the study.

Modified Intention to Treat (mITT) Cohort: Contacts who are SARS-CoV-2 negative by PCR at the baseline visit.

mITT Sensitivity Cohort: Contacts in the mITT cohort who are SARS-CoV-2 negative by PCR at the day 1-3 visits. Participants who are SARS-CoV-2 negative on two of the three days, without a SARS-CoV-2 positive result, will be included in this cohort.

Seronegative Cohort: If a validated, sensitive and specific assay is available for antibody testing, this cohort will include all mITT cohort participants who are antibody negative at baseline.

Infected Cohort: Contacts who are SARS-CoV-2 positive by PCR at the baseline visit.

PK Cohort: Participants from the DBS Sub-study with at least 1 interpretable PK sample

Household Cohort: All enrolled index cases and their household contacts. Enrolled indexes are enrolled in either the PEP Study or the companion Early Treatment Study.

Index Cohort: All enrolled index cases.

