7. EFFICACY/EFFECTIVENESS ANALYSES

7.1. EFFICACY ANALYSES

Final (as opposed to interim) efficacy analyses will be stratified (baseline hazard) for enrollment site and contact type and adjusted by baseline variables as noted in each section below.

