PCR tests not meeting these criteria will be referred to as negative. The endpoint will be defined as the number of days from the first positive test until virus is no longer detected (a negative test has been observed with no positive tests following). Censoring will be indicated if the participant is still shedding on day 14. Participants who have a COVID-19 related hospitalization or death will be assumed to shed through day 14 and would have their days of shedding censored as if they had been observed through day 14.

Analysis Details: We will use a Cox Proportional Hazards model with robust standard errors to estimate the hazard ratio and corresponding 95% confidence interval and Wald test statistic. Robust confidence intervals and p-values will be displayed. This analysis represents a subset selected post-randomization and therefore requires adjustment for confounders. Due to lack of known confounders early in the epidemic, we propose that the list of baseline descriptors be assessed individually for their association with the primary endpoint. Those associated univariably with $p < 0.10$ will be included in this analysis. A hazard ratio greater than 1 (treatment/control) indicates efficacy of the intervention in shortening shedding.

Prevention of COVID-19 diagnosis

Objective: To test the efficacy of HCQ to prevent incident COVID-19.

Outcome: PCR-confirmed COVID-19 diagnosis post start of HCQ therapy through Day 14

Cohort(s): ITT, mITT, Sensitivity, Seronegative, Infected

Definition of Endpoint: COVID-19 is defined as symptomatic disease based on the following criteria with virologic confirmation (RNA PCR Ct \leq 40):

- At least TWO of the following symptoms: Fever ($\geq 38^{\circ}\text{C}$), chills, rigors, myalgia, headache, sore throat, new olfactory and taste disorder(s), OR
- At least ONE of the following symptoms: cough, shortness of breath or difficulty breathing, OR
- Severe respiratory illness with at least 1 of the following:
 - Clinical or radiological evidence of pneumonia, OR
 - Acute respiratory distress syndrome (ARDS)

A participant will be defined as having reached the endpoint if they have the diagnosis above. The time of the endpoint will be the onset of symptoms. Participants who do not have the endpoint will be censored at the last time they were known to be symptom-free. Death and hospitalization will be counted in the endpoint.

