Analysis Details: We will use a Cox Proportional Hazards model with robust standard errors to estimate the hazard ratio and corresponding 95% confidence interval and Wald test statistic. Efficacy will be calculated as 1 minus the hazard calculated from the treatment coefficient. Robust confidence intervals and p-values will be displayed. The following baseline variables will be included to increase precision: presence of metabolic disease (if present in at least 10% of the population), weight, sex, age, and type of contact.

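### The ITT analysis of COVID-19 pools Day 1 PCR-positive and PCR-negative contacts without using Day 1 PCR status; adding it as a stratum is a cheap improvement whose gain depends on assumptions

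*SAP*

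**What the plan says.** SAP section 7.1.2, Prevention of COVID-19 diagnosis, sets the endpoint (symptomatic disease with virologic confirmation, through Day 14) and the analysis sets: "Cohort(s): ITT, mITT, Sensitivity, Seronegative, Infected". SAP section 3.1 defines three of these as follows:

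- ITT: "The ITT Cohort includes all contacts enrolled into the study".
- mITT: "Contacts who are SARS-CoV-2 negative by PCR at the baseline visit".
- Infected: "Contacts who are SARS-CoV-2 positive by PCR at the baseline visit".

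So the ITT row holds both baseline-negative and baseline-positive contacts. The positives stay at risk for the endpoint. Protocol section 8.1 says "Participants who are identified as SARS-CoV-2 positive by PCR at baseline should continue study therapy and study participation", and protocol section 6.1.2 excludes anyone "Symptomatic with subjective fever, cough, or shortness of breath", so most positives enter without the main symptoms and can develop them later.

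For the model, SAP section 7.1 has all final efficacy analyses "stratified (baseline hazard) for enrollment site and contact type". Section 7.1.2 then says "The following baseline variables will be included to increase precision" and names metabolic disease (if common enough), weight, sex, age and contact type. Contact type thus appears as both stratum and covariate, and Day 1 PCR status as neither. The SAP does not say which of the five cohorts leads for this endpoint.

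**The concern.** A contact who is PCR-positive on Day 1 has in general already met the virologic half of the endpoint and needs only symptoms. A negative contact must first become infected, which the SAP puts at 10% in the control arm, and then become symptomatic. The two groups should therefore differ widely in 14-day risk, and none of the listed covariates is likely to separate risk as sharply. The SAP gives precision as its reason for choosing covariates, yet omits the variable likely to add most precision.

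At stake is the efficiency of one pooled estimate. When a strong predictor is left out of a Cox model, the HR that the model targets lies closer to 1 than the HR within each risk group, and the test loses power. Baseline positives also come in household groups, so chance imbalance between arms adds noise that stratification would remove.

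**Working it through.** **The plan's own figures.** None is given for COVID-19. The design figures for the primary infection endpoint reproduce:

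- Participants: 93 / ((0.10 + 0.05)/2) = 93 / 0.075 = 1240 baseline negatives.
- Events: a fixed design at HR 0.5, 90% power and one-sided 0.025 needs 4(1.96 + 1.28)²/(ln 0.5)², about 88. Simulating the SAP Table 1 bounds at 19, 37, 56, 74 and 93 events gives power 0.903 and one-sided error 0.025.

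**Inputs for the check.** From the SAP: 1240 baseline negatives, 1:1 allocation, two-sided 0.05. Assumed, because the documents are silent: 10% of ITT contacts positive on Day 1 (1240/0.90 ≈ 1378 in total, so 138 positive); control 14-day COVID-19 risk 6% in negatives and 50% in positives; HR 0.60 in both groups.

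**Hand calculation.**

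1. Treated risk = 1 − (1 − control risk)^HR. Negatives: 1 − 0.94^0.6 = 0.0364. Positives: 1 − 0.50^0.6 = 0.340.
2. Events, with 620 negatives and 69 positives per arm. Control: 37.2 + 34.5 = 71.7. Treated: 22.6 + 23.5 = 46.1. Total about 118. Positives are 10% of contacts and give 58/118 = 49% of events.
3. Pooled risks: 71.7/689 = 0.1041 and 46.1/689 = 0.0669. Pooled HR ≈ ln(1 − 0.0669)/ln(1 − 0.1041) = 0.63, against 0.60 within each group.
4. Power ≈ Φ(|ln HR| × √(events/4) − 1.96). Unstratified: 0.462 × 5.43 − 1.96 = 0.55, about 71%. Stratified: 0.511 × 5.43 − 1.96 = 0.81, about 79%. Gain: about 8 points.

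**Simulation of the same case.** With independent individuals (4000 replicates), power is 70.5% unstratified and 78.6% stratified. With household randomisation, an assumed household correlation of 0.2 in baseline positivity and a household-robust Wald test (1200 replicates), it goes from 71% to 80% under household mix A of protocol Table 1 and from 66% to 77% under mix C. The gain is therefore about 8 to 11 points.

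**Varying the assumptions.** Rows with a range use 1500 replicates per scenario, independent individuals, 5% to 15% positive, and control risks of 3% to 8% in negatives and 30% to 70% in positives.

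| Assumed effect | Gain from stratifying |
|---|---|
| HR 0.60 in both; 10% positive, risks 6% and 30% | 65.2% to 67.6%: 2.4 points |
| HR 0.60 in both; 5% positive, risks 6% and 30% | 56.9% to 58.2%: 1.3 points |
| HR 0.5 in both | 1.4 to 11.5 points |
| HR 0.6 or 0.7 in both | 0.3 to 23.4 points |
| HR 0.5 in negatives, 0.75 in positives | 0.5 to 20.5 points |
| HR 0.5 in negatives, 1.0 in positives | −3.3 to +0.9 points |

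In the last row, household-clustered runs gave −1 (mix A) and +3 (mix C). The pooled HR is 0.60 to 0.87 with or without the stratum, so stratifying recovers nothing there. A 90% risk in positives, outside the range used, would raise the gain at a common HR to about 16 to 48 points.

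**Type I error.** Null simulations gave one-sided error of 2.6% to 2.8% with and without the stratum.

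**The case against.** The strongest reply is that little is missing. The mITT and Infected cohorts are exactly the two strata, each has its own planned Cox model for this endpoint, and so the HR by baseline status will be reported anyway. This stands, and no further stratum-specific output is needed. It does not make the pooled ITT row efficient.

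Second, omitting the variable is not an error. This also stands. A reader might infer that the ITT HR is biased or its test invalid. The documents do not support that: under randomisation the unstratified HR is a legitimate marginal quantity, the gap from 0.60 to 0.63 is non-collapsibility, and chance imbalance is part of the sampling variance.

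Third, a reader might take a fixed loss of, say, 6 to 12 points as established. The documents give none of the inputs needed. The 50% risk in positives is especially uncertain, since entry excludes contacts with the main symptoms.

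Fourth, the protocol describes PEP as preventing infection, so an effect confined to uninfected contacts is a natural scenario. The dilution then comes from including positives, and no stratum can undo it.

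Fifth, the Day 1 swab is self-collected at home. A contact without a usable result belongs to neither stratum and could drop out of an ITT model if no rule is written.

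**Conclusion.** The point holds as a cheap improvement to one cohort row of one secondary endpoint. The ITT COVID-19 model omits Day 1 PCR status, a collected variable that already defines the trial's cohorts. If HCQ acts similarly in both groups, the pooled HR moves modestly toward 1 and power falls: by about 8 to 11 points at 10% positive, risks of 6% and 50% and a common HR of 0.60, and by about 0 to 23 points over a common HR of 0.5 to 0.7 with the wider inputs. If HCQ has no effect in positives, stratifying changes power by about −3 to +3 points. All these sizes rest on assumed inputs.

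A reader might carry the point over to the primary analysis. That would be wrong, because the primary analysis uses the mITT cohort, in which every contact is negative at baseline.

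**What to change.** In SAP section 7.1.2, Prevention of COVID-19 diagnosis, state that the ITT model is additionally stratified on the baseline hazard by Day 1 PCR status (positive, negative, missing or unusable), beside site and contact type. The third category keeps every ITT participant in the analysis. Refer to the mITT and Infected analyses for the HRs by baseline status.

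The cost is one sentence of SAP text and one stratum term, with no new data. The downside is small: the need to handle missing results, and up to about 3 points of power if HCQ has no effect in baseline positives.

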
 To test the efficacy of HCQ (400 mg orally daily for 3 days then 200 mg orally daily for an additional 11 days, to complete 14 days) to prevent incident SARS-CoV-2 infection 2 weeks after completing therapy, compared to ascorbic acid among contacts of persons with SARS-CoV-2 infection 	
 PCR-confirmed SARS-CoV-2 infection (self-collected samples collected daily Day 1 through Day 14 and collected 2 weeks after cessation of treatment [i.e., Day 28])

 To test the efficacy of HCQ to shorten the duration of SARS-CoV-2 shedding among those with SARS-CoV-2 infection in the HCQ PEP group 	
 SARS-CoV-2 viral shedding by PCR

 To test the efficacy of HCQ to prevent incident COVID-19 	
 PCR-confirmed COVID-19 diagnosis post start of HCQ therapy
Exploratory	

 To conduct SARS-CoV-2 viral genotyping to assess the impact of HCQ on viral resistance to HCQ PEP 	
 Viral genotyping of SARS-CoV-2 in a subset of treated study participants who develop infection

 To assess adherence to HCQ PEP 	
 Self-reported daily dosing and study therapy concentration (if in sub-study) in study participants

 To evaluate the pharmacokinetics (PK) of HCQ by infection status 	
 HCQ blood concentration

 To assess if there is an association between PK of HCQ and the efficacy and safety endpoints evaluated 	
 HCQ blood concentration, tolerability, and efficacy

 To evaluate if SARS-CoV-2 viral load in the index case is associated with SARS-CoV-2 infection in the contact 	
 SARS-CoV-2 semiquantitative PCR and genotyping

 To test the efficacy of HCQ to shorten the magnitude of SARS-CoV-2 shedding among those with SARS- 	
 Daily SARS-CoV-2 semiquantitative PCR

CoV-2 infection in the HCQ PEP group	

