7.1.1. Primary efficacy analyses

Objective: To estimate the efficacy of HCQ (400 mg orally daily for 3 days then 200 mg orally daily for an additional 11 days, to complete 14 days) to prevent incident SARS-CoV-2 infection, compared to ascorbic acid among contacts of persons with SARS-CoV-2 infection.

Outcome: Polymerase chain reaction (PCR)-confirmed SARS-CoV-2 infection through Day 14

Cohorts: mITT Cohort, Sensitivity Cohort

Definition of Endpoint: An endpoint defining PCR test is defined as one with either concordant results or $Ct \leq 40$ and will be referred to as positive test for this analysis. PCR tests not meeting these criteria will be referred to as negative. A participant will be defined as having reached the endpoint on the midpoint between the days of collection of their first positive result and last negative result (prior to the positive result) in the first 13 days of follow-up. Participants who have confirmed COVID-19 through external evaluation in the first 13 days (e.g. hospital or clinical assessment) will be defined as having reached the endpoint at the midpoint between the last prior negative test and the day of the external diagnosis. Participants who do not reach the endpoint will have their follow-up censored at their last negative RNA test. Any uncertainty in final endpoint determination will be resolved by the blinded Endpoint Adjudication Committee.

Analysis Details:

The primary analysis will be performed on the mITT Cohort. A sensitivity analysis will be performed on the Sensitivity Cohort to account for potential missed infections at day 1.

We will use a Cox Proportional Hazards model with robust standard errors to estimate the hazard ratio and corresponding 95% confidence interval and Wald test statistic. Efficacy will be calculated as 1 minus the hazard ratio (treatment/control) from the treatment coefficient. Robust confidence intervals and p-values will be displayed. Per FDA guidance on prevention studies, the following variables will be included to increase precision: quarantine status, sex, and age of contact.

The number of evaluable participants per arm will be displayed (defined as participants with at least one PCR test result or external diagnosis) by arm with person-days of follow-up and number of endpoints per arm and prevalence of endpoints (number reached endpoint/number evaluable) with a 95% confidence interval calculated using exact binomial confidence intervals.

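### The COVID-19 model for the Infected Cohort leaves out the Day 1 PCR Ct value; adding it is a cheap, optional gain in power if Ct is prognostic

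*SAP*

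**What the plan says.** The COVID-19 diagnosis analysis in SAP 7.1.2 names its populations as "Cohort(s): ITT, mITT, Sensitivity, Seronegative, Infected". SAP 3.1 defines the last of these: "Infected Cohort: Contacts who are SARS-CoV-2 positive by PCR at the baseline visit".

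The model is the same for all five: "We will use a Cox Proportional Hazards model with robust standard errors to estimate the hazard ratio". The covariates are also the same: "The following baseline variables will be included to increase precision: presence of metabolic disease" (only if at least 10% of the population has it), followed by "weight, sex, age, and type of contact". SAP 7.1 adds that final efficacy analyses "will be stratified (baseline hazard) for enrollment site and contact type and adjusted by baseline variables as noted in each section below", so adjustment is limited to what each section lists. Ct and viral load are not in the 7.1.2 list, nor among the baseline variables in SAP Section 6.

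The value itself should exist. The Protocol's Schedule of Activities has a mid-nasal swab on Day 1, and Protocol 9.1.1 lists that swab before the first dose. Protocol Section 4 plans "Daily SARS-CoV-2 semiquantitative PCR" as an exploratory endpoint. The SAP uses Ct in its rules for a positive test: "An endpoint defining PCR test is defined as one with either concordant results or" a Ct of 40 or below in 7.1.1. For shedding, 7.1.2 spells this out as both targets found, or one target found within that limit.

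**The concern.** The list was written for five cohorts together, and Ct cannot be used where participants are PCR-negative at baseline. In the Infected Cohort everyone has tested positive, so positive/negative status is constant and cannot serve as a covariate, while the strength of the signal varies. That signal is a measurement, scheduled before treatment, of the infection whose progression is the outcome. The SAP's stated purpose for the covariates is precision, so this is a natural candidate to consider.

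What is at stake is power, and how the hazard ratio is read, in one cohort of one secondary analysis. The primary endpoint, the sample size and the interim bounds are not touched.

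**Working it through.** **The plan's own figures.** SAP 2.4 gives 93 events and 1240 baseline-negative participants.
- Fixed-design Schoenfeld count: 4 × (1.960 + 1.282)² / (ln 0.5)² = 87.5, so 88 events.
- Simulating the five-look bounds of SAP Table 1 at 93 events gives power 90.2% and one-sided alpha 0.0253.
- Participants: 93 / ((0.10 + 0.05)/2) = 93 / 0.075 = 1240.

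The design reproduces, but it concerns the baseline-negative primary analysis. The documents give no size, event count or power for the Infected Cohort.

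**Assumptions for this cohort (none from the documents).** Exponential times to Day 14; a standardised baseline Ct acting log-linearly on the hazard; true hazard ratio 0.5 given Ct; two-sided 0.05; independent participants; no other covariates or strata. As a guide to scale, a log-HR of 0.74 per SD corresponds to a correlation with log time of 0.74 / √(0.74² + 1.645) = 0.50.

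**Power by simulation, true hazard ratio 0.5.**

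| Model | n | Control risk | Ct log-HR per SD | Without Ct | With Ct | Gain (points) |
|---|---|---|---|---|---|---|
| Cox | 200 | 40% | 0 | 77% | 77% | 0 |
| Cox | 200 | 40% | ln 1.5 = 0.41 | 73% | 75% | 3 |
| Cox | 200 | 40% | ln 2 = 0.69 | 69% | 77% | 8 |
| Cox | 200 | 60% | 0.41 | 90% | 92% | 2 |
| Cox | 200 | 60% | 0.69 | 85% | 94% | 9 |
| Cox | 100 | 50% | 0.74 | 43% | 53% | 10 |
| Cox | 100 | 30% | 0.74 | 30% | 36% | 6 |
| Exponential, robust SE | 200 | 50% | 0.3 | 85% | 86% | 1 |
| Exponential, robust SE | 200 | 50% | 0.5 | 82% | 87% | 5 |
| Exponential, robust SE | 200 | 50% | 0.7 | 79% | 87% | 8 |
| Exponential, robust SE | 100 | 50% | 0.5 | 56% | 61% | 5 |
| Exponential, robust SE | 100 | 50% | 0.7 | 53% | 62% | 9 |

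Gains are taken before rounding. A separate Cox check at n = 150, log-HR 0.6 and control risk 30 to 50% gave a gain of 5 to 9 points. A very strong Ct effect (ln 3 = 1.10 per SD, n = 200) gave 18 points at 40% risk and 21 at 60%. A setting with 20% control risk was numerically unstable and is left out. At n = 100 and 50% risk the two models differ by about 10 points in power level but agree on the gain (9 and 10), so rely on the gain and not the level.

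**Where the gain comes from.** Take the Cox case with n = 200, 40% risk and log-HR 0.69.
- Without Ct: mean HR 0.531, model SE of log HR 0.261. Ratio: |ln 0.531| / 0.261 = 0.633 / 0.261 = 2.43.
- With Ct: mean HR 0.499, model SE 0.263. Ratio: 0.695 / 0.263 = 2.64.

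The numerator rises by about 10% (0.695 / 0.633) and the SE does not fall. The empirical SEs, 0.261 and 0.269, say the same. The two models estimate different quantities: the hazard ratio is non-collapsible, and the one without Ct is the more marginal.

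**Size of the shift.** At a conditional HR of 0.5 the HR without Ct averaged 0.52 to 0.54 (n = 150, log-HR 0.6), 0.53 (n = 200, 40% risk, 0.69), and 0.55 both at n = 200 with 60% risk and 0.69 and at n = 100 with 50% risk and 0.74.

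**Null case.** With a treatment HR of 1.0 (n = 200, 40% risk), the mean HR stayed between 0.99 and 1.01 with or without Ct. The rejection rate in the direction of benefit was 0.021 to 0.024 without Ct and 0.021 to 0.029 with it, against a nominal 0.025.

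**The case against.** The strongest reply is that this is a choice and not an error. One prespecified list keeps the five adjusted hazard ratios comparable, and Ct cannot enter the PCR-negative cohorts. Nothing in the documents says that baseline Ct predicts symptoms: Protocol 3.2.6 links viral quantity to transmission, and SAP 7.1.2 itself notes how little was known about confounders early in the epidemic. Contacts enrol without fever, cough or shortness of breath and less than 4 days after last exposure. A weak Day 1 signal could therefore be an early, rising infection or a fading one, and a single linear term cannot separate the two. The simulations also omit the covariates already listed, the strata and household clustering, so the increment over the actual SAP model has not been estimated.

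All of this stands as a limit on the size of the benefit. It does not make the addition harmful: if Ct is uninformative, power is essentially unchanged. The documents also give some reason to think that Ct may matter. The COVID-19 endpoint requires PCR confirmation with Ct at or below 40, and SAP 7.1.3 runs a sensitivity analysis that counts inconclusive tests with Ct above 38 as negative.

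A reader might infer three stronger things that the documents and the check do not support.
- That Ct defines the cohort. A positive baseline PCR does, and concordant results qualify without the Ct limit.
- That the plan accepts a larger standard error. In the Cox runs the SE of log HR was no smaller with Ct.
- That the planned hazard ratio is wrong or its test invalid. The cohort is fixed by a baseline swab within randomised arms, type I error is kept, and nothing shifts if the treatment has no effect or Ct is not prognostic.

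**Conclusion.** The point holds as a minor, low-cost improvement to one cohort of one secondary analysis. The SAP does not use the Day 1 Ct in the Infected Cohort's COVID-19 model, although the value should be available for every member. The planned analysis is valid.

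If Ct is prognostic and the treatment effect is not null, the omission gives a hazard ratio nearer 1 than the Ct-conditional one. It also costs roughly 0 to 2 points of power for a weak Ct effect and about 5 to 10 for a moderate one (log-HR 0.5 to 0.7 per SD, 100 to 200 contacts, 30 to 50% control risk, HR 0.5). Prognostic strength, cohort size, event risk and treatment effect are all assumed, so confidence in the size is low. Confidence in the direction, given a prognostic Ct and a real effect, is good.

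**What to change.** In SAP 7.1.2, under the COVID-19 diagnosis analysis, add one sentence for the Infected Cohort only: the Day 1 Ct enters as a continuous covariate, taken from one pre-named PCR target, or from the other target when only that one is detected. Keep the listed covariates and the site and contact-type strata. Leave the other four cohorts as they are. Write this in before unblinding, since a later addition would look data-driven.

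No new data are needed. The cost is one degree of freedom, the need to name the target, and an adjusted hazard ratio that does not condition on quite the same variables as those of the other four cohorts.
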